8 SAFETY ANALYSIS

All safety analyses will use the Safety population, unless otherwise specified. All safety assessments will be summarized by treatment group. There may, in addition, be separate analyses of groupings of adverse events, laboratory values, or procedures of special interest.

Safety analyses will be summarized by treatment group (e.g., N, mean, median, SD and proportions, as appropriate). All analyses will be summarized by Study Day, as appropriate. Analyses will also be provided for the time periods during the treatment period and also for the time periods after the treatment ends. Factors related to post-treatment care and activities will be included in summaries of post-baseline distributions. All changes will be calculated relative to randomization date/time (as all subjects are on standard of care treatment as of the randomization date/time). Additional summaries of changes relative to ELAD start date/time will be provided for selected analyses. For comparative purpose, the Control group will be summarized by changes relative to End of Study Day 2, as this most closely mimics the time of initiation of ELAD treatment in those subjects randomized to ELAD. If Study Day 2 is missing for Control subjects, the last non-missing visit before Study Day 2 will be used for analysis.

Summaries of quantitative variables will include distributions by a clinically relevant discretization of each of the variables, along with computation of the mean, median, SD, minimum, and maximum. All data captured on the CRF will be presented in individual listings.

If a data point is collected more than once at the same visit, the last measurement will be used for analysis.

8.1 HANDLING MISSING DATA

Summaries will be based on observed data only, except for the following:

- Treatment-emergent derivation: If an AE start date is incomplete or completely missing, the following imputation rules apply to determine if an AE is treatment-emergent:
 - If only the year and month are reported, and they are the same year and month as the randomization date, then the day will be imputed to be the same as the randomization day, and the AE start time will be imputed to be the randomization time. Otherwise, the day will be imputed to the first day of the month;
 - If only the year is reported, and it is the same year as the randomization date, then the day and month will be imputed to be the same as the randomization day and month, and the AE start time will be imputed to be the randomization time. Otherwise, the day and month will be imputed to January 1st;
 - If the date is completely missing, then the start date/time will be imputed to be the same as the randomization date/time;
 - If only the AE start time is missing, and the AE start date is the same as the randomization start date, then the AE start time will be imputed to be the same as the randomization time. Otherwise, the AE start time will not be imputed.

For analyses of AE onset relative to ELAD treatment, the same imputation rules will be applied for analysis using ELAD start date/time instead of randomization start date/time.

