8.3 ADVERSE EVENTS

The number and percent of subjects with treatment-emergent adverse events (TEAEs), TEAEs leading to ELAD discontinuation, TEAEs leading to ELAD treatment interruptions, TEAEs classified by their highest relationship to study drug, and TEAEs classified by their maximum severity, will be summarized by treatment group and by MedDRA System Organ Class and Preferred Term. Individual listings of all TESAEs, all deaths, and all TEAEs leading to ELAD discontinuation/interruption will be prepared.

Treatment-emergent adverse events are defined as those AEs with an onset date/time on or after the randomization date/time. The rationale for this is that subjects in both treatment groups are receiving standard of care at the time of Randomization. In addition summary tables of TEAEs and TESAEs will be presented based on treatment and post-treatment study periods. The study periods used in analysis for ELAD-treated subjects will be defined as Pre-ELAD (Randomization date/time to ELAD start date/time), ELAD Treatment (ELAD start date/time to Study Day 7), D8-D14 (Study Day 8 to Study Day 14) and D15-D91 (Study Day 15 to Study Day 91); and for Control subjects, Rand-D2 (Randomization date/time to Study Day 2), D3-D7 (Study Day 3 to Study Day 7), D8-D14 (Study Day 8 to Study Day 14) and D15-D91 (Study Day 15 to Study Day 91). Additional summaries of TEAEs that started between Randomization and ELAD treatment start, and TEAEs/TESAEs that started after ELAD treatment start will be presented by MedDRA System Organ Class and Preferred Term for subjects in the ELAD treatment group. For comparison purposes within these summary tables, TEAEs that started between Randomization and Study Day 2, and TEAEs/TESAEs that started after Study Day 2 will be presented for subjects in the Control treatment group.

Treatment-emergent adverse events will be coded using Medical Dictionary for Regulatory Activities (MedDRA) (Version 18.1) and incidences will be compared between treatment groups using MedDRA Preferred Terms within System Organ Classes. Subjects will only be counted once within each level of summarization.

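### In the AE summaries split at ELAD start (ELAD) and Study Day 2 (Control), undated onsets are anchored to ELAD start in one arm and, by default, to randomization in the other

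*SAP*

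**What the plan says.** SAP 8.1 (Handling Missing Data) opens with "Summaries will be based on observed data only, except for the following" and then lists rules for incomplete AE start dates. The default applies to both arms: "If the date is completely missing, then the start date/time will be imputed to be the same as the randomization date/time". A date with only month and year, or only the year, goes to randomization if it matches the randomization month or year. Otherwise it goes to the first of the month or to January 1st. The section ends with a single variant: for onset relative to ELAD treatment, "the same imputation rules will be applied for analysis using ELAD start date/time instead of randomization start date/time".

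SAP 8.3 (Adverse Events) divides ELAD follow-up into a pre-ELAD period that ends at ELAD start and an ELAD Treatment period from there to Study Day 7. Control is divided into Rand-D2 and D3-D7. Further summaries split ELAD subjects at ELAD start, and for comparison "TEAEs/TESAEs that started after Study Day 2 will be presented for subjects in the Control treatment group".

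SAP 8.2 sets the treatment start for standard-of-care subjects at the randomization date. The introduction to SAP Section 8 names End of Study Day 2 as the Control time closest to ELAD initiation, but only for changes from baseline.

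**The concern.** The split tables are meant to separate AEs that arose before device exposure from those that arose after it, with a matched split in Control. Their boundaries are matched, but the rule that places undated events around those boundaries is not. The ELAD anchor is moved to the boundary, while the only anchor written for Control is randomization, up to two days before it.

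Identical undated events can then raise ELAD's post-start incidence and Control's pre-split incidence. The difference would come from the imputation rule and not from the treatment. SAP 1.2.1 puts safety within the primary objective, and SAP 8.3 says AE incidences will be compared between groups, so a one-sided rule should not be left in a planned between-arm table.

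**Working it through.** The plan gives no figure to reproduce. The check applies the 8.1 rules to the same incomplete date in each arm and reads off the 8.3 period.

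**Inputs**
- ELAD anchor in these analyses: ELAD start (SAP 8.1). Under SAP 3.4, subjects who never start ELAD are counted with Control, so everyone in the ELAD column has this time.
- Control anchor: randomization (SAP 8.1 default, with no Study Day 2 variant).
- Events imputed exactly to ELAD start are taken as on treatment, following the on-or-after convention that SAP 8.3 uses for TEAEs at randomization.
- The calendar dates are assumed for illustration. End of Study Day 2 is taken as 08:00 two days after randomization, in line with the study-day definitions in Protocol 5.4 and 5.5.1.

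**Case A: randomization 10 March 15:00, ELAD start 12 March 09:00**

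| Recorded onset | ELAD arm | Control arm |
|---|---|---|
| Wholly missing | 12 March 09:00, ELAD Treatment | 10 March 15:00, Rand-D2 |
| Year only, same year | 12 March 09:00, ELAD Treatment | 10 March 15:00, Rand-D2 |
| March only | 12 March 09:00, ELAD Treatment | 10 March 15:00, Rand-D2 |
| April only | 1 April, after the split | 1 April, after the split |

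**Case B: randomization 31 March 15:00, ELAD start 2 April 09:00**

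| Recorded onset | ELAD arm | Control arm |
|---|---|---|
| Wholly missing | 2 April 09:00, ELAD Treatment | 31 March 15:00, Rand-D2 |
| Year only, same year | 2 April 09:00, ELAD Treatment | 31 March 15:00, Rand-D2 |
| April only | 2 April 09:00, ELAD Treatment | 1 April 00:00, Rand-D2 |
| March only | 1 March 00:00, before randomization | 31 March 15:00, Rand-D2 |

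Three things follow.
1. Wholly missing dates, and partial dates that share the ELAD-start month or year, go to opposite sides of the split in the two arms.
2. Month-only dates later than the month of ELAD start go to the first of that month in both arms, so no asymmetry arises.
3. If randomization and ELAD start fall in different months, an AE dated only to the randomization month is moved to before randomization in the ELAD arm. It then lies in none of the 8.3 periods.

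**Check of the remedy.** With Control anchored at End of Study Day 2, the events in the first three rows of each table move to 12 March 08:00 (Case A) or 2 April 08:00 (Case B). That time is still on Study Day 2, so read literally it remains in Rand-D2 and is not after Study Day 2. The arms match only if events imputed to the anchor go to the later period in both. The March-only event in Case B would go to 1 March in Control as well, so a floor at randomization is also needed.

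**The case against.** **The Control rule is inferred from silence.** The SAP never states that randomization is the Control anchor in the split tables, and Section 8 already treats End of Study Day 2 as the counterpart of ELAD start. This is fair. However, that statement concerns changes from baseline, while 8.1 and 8.2 give Control no reference time other than randomization. If the default is held not to carry over, the Control rule is undefined, and the same sentence is needed.

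**On-treatment placement depends on a tie rule.** An event imputed to ELAD start sits on the shared edge of two periods, and one summary counts only events after the start. If such ties went to the earlier period, wholly missing dates would fall before the split in both arms. This stands as a qualification. On that reading, though, moving the anchor to ELAD start would achieve nothing for those dates, so the on-treatment reading is the more natural one. The rule should be written down either way.

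**Undated onsets should be rare.** Protocol Section 9 requires the onset of every AE to be documented, and SAP Section 9 runs edit checks until queries are resolved. This stands and supports a small effect.

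**ELAD placement will often be right.** Most of the 91 days follow ELAD start, so many undated events did begin after it. That is true of Control and Study Day 2 as well, which is why the arms need the same rule.

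**The tilt is against ELAD, so it hides no harm.** This holds for the post-start tables. In the pre-start tables the tilt is reversed, and a cautious rule applied to one arm only still distorts the comparison.

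**Conclusion.** The point holds for the additional and period-based AE summaries that set ELAD start against Study Day 2. Followed literally, 8.1 treats the same undated event differently by arm and tilts these tables against ELAD. This rests on the randomization default carrying over to Control and on the on-or-after convention applying at ELAD start.

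The size is unknown and probably small. It depends on how many AEs lack usable onset dates, which the documents do not say. Multiplying an assumed AE count by an assumed missing share would not give it either: 8.3 counts each subject once per level, and later-month partial dates do not contribute.

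A reader might infer more than the documents support:
- That the main safety comparison is biased. The overall TEAE tables use randomization in both arms. The infection, fluid and bleeding tables (SAP 8.3.1) start with a Randomization-to-Day-7 period in both arms, which spans the split.
- That ELAD's pre-start period is emptied and Control's filled. Events with complete dates do not move.
- That the medication tables in SAP 8.4 share the fault because they reuse the 8.3 periods. The 8.1 rules cover AE start dates only.

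Overall survival is not touched.

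**What to change.** Add to SAP 8.1, after the sentence on ELAD start:

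*For Control subjects in these analyses the same rules apply using the End of Study Day 2 date/time in place of the ELAD start date/time. In both arms an event imputed to the anchor is assigned to the later period (ELAD Treatment or D3-D7, and the after-ELAD-start or after-Study-Day-2 tables). No imputed date may precede randomization solely because of the change of anchor.*

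All three parts are needed, since the anchor alone leaves Control events on Study Day 2. The ELAD anchor is unchanged, and the Control anchor matches the one Section 8 already uses for changes from baseline. The cost is a short SAP addition and one programming parameter with its tie and floor conditions. No new data are required.

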8.2 EXTENT OF EXPOSURE

For subjects who receive ELAD treatment, the duration of ELAD treatment will be calculated based on the start date/time of ELAD treatment (defined as the time at which the ultrafiltrate pump is switched on for the first time) to the end date/time of ELAD treatment (defined as the time at which the Ultrafiltrate pump is switched off for the last time). A second analysis will exclude any off-time gaps >6 hours (e.g., for cartridge exchange). The duration of ELAD treatment will be summarized by descriptive statistics and by proportions of subjects receiving <72 hours, 72 to <96 hours, and ≥96 hours of treatment. The mean time from Randomization to ELAD treatment initiation will also be presented using descriptive statistics.

For subjects who receive SOC treatment, the treatment start date will be the same as the randomization date.

Additionally, the proportions of subjects who completed at least 72 hours and 120 hours on ELAD treatment will be presented, along with the reason for discontinuation of ELAD treatment.

8.3 ADVERSE EVENTS

The number and percent of subjects with treatment-emergent adverse events (TEAEs), TEAEs leading to ELAD discontinuation, TEAEs leading to ELAD treatment interruptions, TEAEs classified by their highest relationship to study drug, and TEAEs classified by their maximum severity, will be summarized by treatment group and by MedDRA System Organ Class and Preferred Term. Individual listings of all TESAEs, all deaths, and all TEAEs leading to ELAD discontinuation/interruption will be prepared.

Treatment-emergent adverse events are defined as those AEs with an onset date/time on or after the randomization date/time. The rationale for this is that subjects in both treatment groups are receiving standard of care at the time of Randomization. In addition summary tables of TEAEs and TESAEs will be presented based on treatment and post-treatment study periods. The study periods used in analysis for ELAD-treated subjects will be defined as Pre-ELAD (Randomization date/time to ELAD start date/time), ELAD Treatment (ELAD start date/time to Study Day 7), D8-D14 (Study Day 8 to Study Day 14) and D15-D91 (Study Day 15 to Study Day 91); and for Control subjects, Rand-D2 (Randomization date/time to Study Day 2), D3-D7 (Study Day 3 to Study Day 7), D8-D14 (Study Day 8 to Study Day 14) and D15-D91 (Study Day 15 to Study Day 91). Additional summaries of TEAEs that started between Randomization and ELAD treatment start, and TEAEs/TESAEs that started after ELAD treatment start will be presented by MedDRA System Organ Class and Preferred Term for subjects in the ELAD treatment group. For comparison purposes within these summary tables, TEAEs that started between Randomization and Study Day 2, and TEAEs/TESAEs that started after Study Day 2 will be presented for subjects in the Control treatment group.

Treatment-emergent adverse events will be coded using Medical Dictionary for Regulatory Activities (MedDRA) (Version 18.1) and incidences will be compared between treatment groups using MedDRA Preferred Terms within System Organ Classes. Subjects will only be counted once within each level of summarization.

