5.4 STUDY TREATMENT

Study Day 1 begins at the time of Randomization when protocol-specified standard of care (SOC) guidelines must be followed and concludes following the next morning's SOC lab draw.

Note: The SOC lab draw may be adjusted in order to initiate ELAD treatment within a 6-hour window to limit blood draws. Study Day 1, therefore, will be less than 24 hours. Study Day 91 is the final study day. All subjects are enrolled into the study with the expectation of completing all 91 days of the study.

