5.4.3.1.2 ELAD Treatment Duration

Subjects randomized to receive ELAD will be treated with ELAD for a minimum of 3 days (72 hours), unless discontinuation criteria are met (See [Section 3](#)). At the end of 3 days (72 hours), a total bilirubin measurement must be taken. If the total bilirubin has increased by 25% or more from the measurement within 6 hours prior to initiation of ELAD treatment, ELAD treatment must be discontinued. If the bilirubin has not increased by 25% then treatment should continue to a maximum of 5 days (120 hours) regardless of treatment interruption (see [Section 6.6](#)). Bilirubin should be measured at least 12 hours after any procedure known to artificially alter serum bilirubin (e.g. administration of PRBCs, plasma exchange).

Subjects randomized to receive ELAD treatment will also receive standard of care therapy, and will receive medical treatment in accordance with the SOC guidelines as delineated in [Section 5.4.1](#) of this protocol and those of the institution. For overall ranges of the durations of ELAD treatments from past trials (presented in hours) see the [Investigator's Brochure](#).

5.4.3.2 ***Control Treatment Start***

Subjects randomized to Control Treatment will initiate treatment in accord with the protocol-defined standards of care immediately following randomization.

The clinical, laboratory, and hemodynamic assessments will be performed at specified intervals during the study treatment period for both the ELAD and Control groups. An overview of evaluations during study treatment is presented in [Table 2](#) for Control subjects and [Table 3](#) for ELAD subjects.

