5.5 EVALUATIONS WHILE ON TREATMENT

All evaluations in this section are for both ELAD and Control subjects, unless specified otherwise.

5.5.1 Daily Evaluations through End of Study Day 7

The following procedures will be performed daily through End of Study Day 7, based on 24-hour periods following the End of Study Day 1, and must be performed a minimum of 12 hours apart and, if specified, either within the defined time window or during the Study Day. Any subject discharged from the hospital prior to End of Study Day 7 must return to the study site for the End of Study Day 7 evaluation only (+2 days). It is not necessary to have outpatients return for daily assessments. There may be instances where the ELAD treatment period is delayed; therefore daily evaluations may be extended beyond End of Study Day 7. Additional eCRFs may be added in this situation. See [Table 2](#) for evaluations schedules for Control subjects and [Table 3](#) for ELAD subjects:

- Physical examination (performed by a Physician, Physician Assistant, or Nurse Practitioner if within the scope of practice for institution)
- Vital signs (blood pressure, heart rate, respiration rate, temperature)
- Encephalopathy stage [West Haven Criteria, performed by a study physician, Physician Assistant, or Nurse Practitioner if within the scope of practice for institution (Refer to [Appendix A](#))] unless subject is sedated
- Routine laboratory evaluations: BUN, creatinine, glucose, sodium, potassium, chloride, carbon dioxide (or bicarbonate), calcium, magnesium, phosphate, ALT, AST, bilirubin (total/direct), albumin, total protein, alkaline phosphatase
- Additional laboratory evaluations: ammonia, lactate, α -fetoprotein, lactate dehydrogenase (LDH)
- Complete Blood Count (CBC): white blood cell count (WBC), hematocrit, hemoglobin, and platelets
- Blood collection for outside analysis (consented subjects at participating centers only - at End of Study Days 3, 5, and 7) (See [Section 5.6.3](#))
- Blood culture samples $\times 2$ – at End of Study Day 2 and End of Study Day 4 for Control subjects, or within 6 hours prior to ELAD treatment start and Hours 48 and 96 of treatment for ELAD subjects
- Ultrafiltrate samples must be drawn as described in [Section 5.6.2](#) and [Section 5.6.4](#).
- PT, PTT, and INR (If heparin is administered, PTT will be assayed in accord with the standard anticoagulation therapy protocol at the site.)

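### The SAP's ELAD Treatment adverse-event period ends at Study Day 7 whatever the pump-stop time, so it does not separate on-device from off-device events

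*SAP*

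**What the plan says.** SAP 8.3 states that "summary tables of TEAEs and TESAEs will be presented based on treatment and post-treatment study periods". In the ELAD arm the periods are a pre-ELAD interval, then "ELAD Treatment (ELAD start date/time to Study Day 7", then "D8-D14 (Study Day 8 to Study Day 14) and D15-D91 (Study Day 15 to Study Day 91". Control has randomization to Study Day 2, Study Days 3 to 7, and the same two later periods. No rule covers a subject who is still on ELAD after Study Day 7. SAP 8.4 takes over these periods for concomitant medications and blood products.

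The timing comes mainly from the protocol:

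- Section 5.5.1 sets the Study Day clock, "based on 24-hour periods following the End of Study Day 1"; section 5.4 adds that "Study Day 1, therefore, will be less than 24 hours".
- Section 5.4.3.1.2 says that, if the 72-hour bilirubin check is passed, "then treatment should continue to a maximum of 5 days (120 hours) regardless of treatment interruption".
- Section 5.5.1 anticipates late courses: "There may be instances where the ELAD treatment period is delayed; therefore daily evaluations may be extended beyond End of Study Day 7". Table 3, footnote 20, provides extra visits if ELAD starts later than End of Study Day 3.
- SAP section 8 anchors the Control arm at End of Study Day 2, "as this most closely mimics the time of initiation of ELAD treatment in those subjects randomized to ELAD".

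Elsewhere the SAP works from the actual stop. Section 7.3.3 ends the ELAD treatment period when ELAD stops. Section 8.2 measures exposure from first to last operation of the ultrafiltrate pump. The bilirubin rule in 7.2.2 accepts the Day 7 value only for subjects who are off treatment. The introduction to section 8 promises safety analyses for the time on treatment and for the time after it has ended.

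**The concern.** A reader of the period tables will take the ELAD Treatment column as what happened on the device and the later columns as what happened afterwards. The fixed end does not guarantee either. An event that starts while the pump is running on Study Day 8 goes into D8-D14. An event that starts two days after an early stop goes into ELAD Treatment. The same applies to medications and blood products in SAP 8.4.

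At stake is whether these tables can describe risk while connected to the circuit. The protocol's Appendix D lists haemorrhage, hypotension and thrombocytopenia among the events that may be related to the cells or the system, so the on-device versus off-device split is one that readers will look for. The primary survival analysis is not affected.

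**Working it through.** The documents state no figure to reproduce here. The check is timeline arithmetic.

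**Inputs**

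- Study Days after the first are 24 h periods counted from End of Study Day 1 (protocol 5.5.1).
- A full course is 120 h and the planned minimum is 72 h (protocol 5.4.3.1.2).
- The Control anchor, used as a stand-in for ELAD start, is End of Study Day 2 (SAP 8).
- The ELAD Treatment window is taken to close at the end of Study Day 7. The SAP does not say start or end of that day. The end is consistent with the next period opening on Study Day 8, and it is the reading that gives the least overrun.

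**Formulas** (hours from End of Study Day 1)

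- End of Study Day k = 24 × (k − 1), so End of Study Day 7 = 24 × 6 = 144 h.
- Stop = start + course length, for an uninterrupted course.
- On-device hours falling in D8-D14 = max(0, stop − 144).
- Off-device hours counted as ELAD Treatment = max(0, 144 − stop).

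**Latest start that fits the window**

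- 120 h course: 144 − 120 = 24 h, which is End of Study Day 2.
- 96 h course: 144 − 96 = 48 h, which is End of Study Day 3.
- 72 h course: 144 − 72 = 72 h, which is End of Study Day 4.

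**Uninterrupted 120 h course**

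| Start | Start (h) | Stop (h) | On-device hours in D8-D14 | Share of course |
|---|---|---|---|---|
| End of Study Day 2 | 24 | 144 | 0 | 0% |
| Mid-Study Day 3 | 36 | 156 | 12 | 12/120 = 10% |
| End of Study Day 3 | 48 | 168 | 24 | 24/120 = 20% |
| End of Study Day 4 | 72 | 192 | 48 | 48/120 = 40% |

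**Opposite direction**

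A 72 h course started at End of Study Day 2 stops at 24 + 72 = 96 h, which is End of Study Day 5. The remaining 144 − 96 = 48 h are off-device but counted as ELAD Treatment.

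**Variant with calendar Study Days**

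If randomization is at clock hour h on Day 1, the end of Day 7 is 168 − h hours after randomization. The latest start for a 120 h course is then 168 − h − 120 = 48 − h hours after randomization. For h from 0 to 24 this runs from 48 h down to 24 h, so the conclusion is unchanged.

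**Interruptions**

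Protocol 6.6 lets the treatment period be extended after an interruption of more than 24 h, up to 120 treatment hours in total, with at most 72 h between cartridge sets. The discontinuation list (protocol section 3, repeated in SAP section 2) sets a maximum of 120 hours inside five 24-hour periods whatever the interruptions. Read literally, the second wording caps elapsed time at 120 h, and interruptions then add nothing to the table above. Under 6.6 they can. The passages must be reconciled before any overrun from interruptions can be given a size.

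**The case against.** The case for leaving the plan alone has real substance.

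- **The fixed end has a purpose.** It lines up with Study Days 3 to 7 in Control. A window that runs to ELAD stop would have a length that depends on post-randomization events, including adverse events that end treatment. This stands, and it argues against replacing the fixed window.
- **No event is lost.** SAP 8.3 also tabulates all events starting after ELAD start (after Study Day 2 in Control) with no Day 7 cut, and events leading to interruption or discontinuation. This limits the damage, but none of those tables separates on-device from off-device onset.
- **The special-interest tables are untouched.** The dedicated bleeding tables in SAP 8.3.1.3 run from randomization to Study Day 7, then Days 8 to 14, 15 to 28 and 29 to 91. They do not use the ELAD Treatment window.
- **Shorter courses fit.** The 72 h and 96 h results above show that only full-length courses lack slack. The protocol's introduction describes three to five days as typical.

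Three stronger readings are tempting, and the documents support none of them. A reader might infer that the rule understates on-device risk, but it errs both ways. A reader might infer that overrun is common. However, the End of Study Day 2 anchor justifies a Control reference time and does not report observed starts; protocol 5.5.1 says only that delays may occur; and no distribution of start times is given. A reader might also combine a start at End of Study Day 3 with a 72 h gap and conclude that 24 + 72 = 96 h fall outside. That depends on protocol 6.6 prevailing over the five-period wording, and on an early gap with the full course delivered. If the gap ran from End of Study Day 7 to End of Study Day 10, only 24 on-device hours would fall outside.

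**Conclusion.** The concern holds as a labelling and definition fault in a supplementary safety split. The ELAD Treatment period in SAP 8.3, and its reuse in 8.4, does not separate on-device from off-device events. It therefore does not deliver what the introduction to SAP 8 promises, and it differs from the actual-stop definitions in 7.3.3 and 8.2.

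Per subject, the size is 12 to 48 on-device hours placed in D8-D14 for an uninterrupted 120 h course started between mid-Study Day 3 and End of Study Day 4. In the other direction it is 48 off-device hours placed in ELAD Treatment for a 72 h course started at End of Study Day 2. These figures assume 24 h Study Days, closure at the end of Study Day 7 and no interruption. The net direction of the error and the number of subjects affected cannot be determined from the documents. The point is minor: worth correcting because it is cheap, but no efficacy conclusion depends on it.

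**What to change.** 1. Keep the fixed Study Day windows in SAP 8.3 and 8.4 for the between-arm comparison. Relabel the ELAD window as ELAD start to Study Day 7, and state that it closes at the end of that day.
2. Add an ELAD-arm table of TEAEs and TESAEs, and of the 8.4 medications and blood products, split at first pump-on and last pump-off as defined in SAP 8.2. Give rates per subject-day, and say whether off-time gaps longer than 6 h count in the denominator, since SAP 8.2 calculates duration both ways.
3. Describe the added table as descriptive only, because the on-device interval can be ended by the events being counted.
4. Reconcile protocol 6.6 with the five-period wording in protocol section 3 and SAP section 2, so that the longest possible course is defined.

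The cost is one extra set of descriptive tables without a matched Control window. No new data are needed, because pump times are already used for exposure in SAP 8.2.
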